Plastic, orthopedic, vascular, and general surgeons commonly encounter infections. These may be post-traumatic (e.g. from a laceration while cooking or at the site of a fracture), embolic (seeding of infection from another source), or due to inoculation (e.g. from a contaminated needle used for intravenous illicit drug use). Regardless of the etiology, these patients present with complex problems that often require repeat debridement prior to reconstruction. Their hospital stays are lengthy, painful (in terms of pain from debridement and dressing changes), and expensive (based on the number of repeat operations required to debride infected tissue). The results of the initial surgical debridement are often uncertain- patient and disease factors contribute to the extent and recurrence of the disease and often surgeons will empirically schedule "second looks" to return to the operating room for a repeat debridement/inspection of the wound prior to performing a reconstruction, in order to avoid experiencing a failed reconstruction due to inadequate debridement. A possible cause for failure of reconstruction is the microbial bioburden present in the open wound. We hypothesize that the continuous irrigation as well as the cycles of wound/exudate disruption afforded by the V.A.C Veraflo technology with Cleanse Choice Dressing will reduce the microbial bioburden and possibly the need for operative debridement by allowing for around-the-clock non-excisional debridement and irrigation.

4) Design & Procedures:

Prospective randomized trial. Two arms, 20 patients in each arm. Study team expects to consent/enroll 60 patients in order to achieve 40 subject for evaluation due to voluntary opt-out, inability to return to OR for "second look" debridement on day 2, medical instability preventing further debridement, etc.

Day 0 - (Prior to surgery):

- Consent, randomization, enrollment

Day 1 (day of first operative debridement):

- Patient arrives in the operating room, anesthesia is induced. The extremity is prepared and draped in standard fashion.

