- Patients age 18 years or older who have an injury or infection for which surgical debridement (in the operating room) followed by VAC application is planned.
- Able to provide informed consent.

Page 4 of 7

- Speak and read English.
- Patients may be immunosuppressed, either through nature of disease or due to medication.
- Patients may be on systemic antibiotics or topical antimicrobials.
- Patients may present with exposed bone or joint space as part of either the debridement or traumatic injury.

Exclusion criteria:

- Patients on therapeutic anticoagulation to treat DVT/PE, atrial fibrillation, etc, for which we would include warfarin, therapeutic heparin or low-molecular-weight heparin, direct oral anticoagulants (e.g. rivaroxaban, dabigatran).
 - Most of these patients are on prophylactic anticoagulation to lower the risk of a DVT (e.g. heparin or enoxaparin subcutaneous injections). We would still like to include those patients in our study. These drugs are given to many hospitalized patients due to their immobility and are not prescribed to the same patients once they are safely living at home again. Additionally, many patients are on aspirin for the coronary prevention factor and we do not even usually hold this prior to surgery (even if someone wanted to, it takes days of waiting to reverse the platelet effects and these are acute wounds/infections). We would also like to include patients on aspirin or clopidogrel (anti-platelet agents), for example.
- 6) Subject Recruitment and Compensation: A maximum of 60 subjects will be consented in order to achieve 40 evaluable subjects. Duke subjects will be introduced by their healthcare team and if interested in participating, will be given more information by the research team. Potential subjects will be screened in the ED or Hospital and identified by an investigator or a member of the research team. An investigator will confirm eligibility criteria and a member of the site study team will notify the sponsor of a potential candidate for the study after the subject has been consented.

There is no subject compensation planned for this study.

7) Consent Process: Subjects will be introduced to the study by their physician and then the study team will provide additional information and consent if subjects are interested in participating in the study. See iRIS consent section for additional consent details. Patients will be approached after permission is granted by a member of the care team.

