Primary endpoint: Bacterial bio-burden as measured by quantitative microbial PCR prior to debridement, immediately following initial debridement, after 2 days of VAC veraflo (or conventional VAC) therapy, and at the time of repeat operative debridements, if needed. We will use the MicroGen PCR platform (DBA Microgen Diagnostics, LLC, Lubbock, TX.) to report on the bacterial burden (reported on a log scale of bacteria per gram) present at the time of debridement.

Exploratory endpoint: Number of operative debridements required prior to reconstruction, number of days until final reconstruction, number of days until

Page 6 of 7

decision is made by surgeon that further debridements are no longer necessary, length of hospital stay, wound surface area.

[name] to do analysis using JMP (SAS) software. Will use t-test for log scale of bacteria per gram.

Power analysis for a one-way ANOVA with 2 groups was conducted to determine a sufficient sample size using an alpha of 0.05, a power of 0.80, and a large effect size (f = 0.40) Based on the aforementioned assumptions, the desired sample size is 25.52. Original funding called for 60 patients, but funding agency subsequently retracted their offer to cover indirect costs, so the sample size was decreased to 40 patients total as the grant now must absorb the indirect costs.

13) Data & Safety Monitoring:

All adverse events related to the study will be signed off on by the PI and reported to the IRB in accordance with Duke and HIPAA policies.

Privacy, Data Storage & Confidentiality: Any data that is stored in paper or non-digital format will be locked in a file cabinet within a controlled access office. The office will be locked when not in use by the study team. All electronic study information will be stored on the secure Surgery Server in the IRB folder for this study with access limited only to the study team. All study information will be stored in accordance with the RDSP for this study.

Confidentiality of subject data will be ensured by de-identification of subject data. During data collection, subject identifiers and relevant data elements will be recorded in the database. Then, study-specific identification numbers will be assigned to each subject. Prior to dissemination of any information in this database beyond the DUMC's secure servers or firewall, all identifiers will be stripped from the database and data will only be referenced by the study-specific identification numbers.

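### The primary t-test gives no rule for a PCR non-detect and leaves the measured baseline burden unused; if non-detects after therapy were treated as missing, a real effect would be diluted

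*Combined protocol and SAP*

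**What the plan says.** Section 12 (Data Analysis & Statistical Considerations) defines the primary endpoint as bacterial burden by quantitative PCR, "reported on a log scale of bacteria per gram", at several time points. The analysis is stated as "Will use t-test for log scale of bacteria per gram". The software is named (JMP), but there is no data-handling rule.

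Neither section 12 nor any other section gives a detection or reporting limit, a value or code for a negative specimen, a censoring or substitution rule, or a missing-data rule. No time point is attached to the t-test, and no baseline adjustment is mentioned.

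Section 4 (Design & Procedures) places specimen 1 before debridement and specimen 2 at its end, both before the device is applied. Specimen 3 is taken at the start of the second operation, the first sample after randomised therapy. The design is "Two arms, 20 patients in each arm". The reasons listed for consenting 60 to obtain 40 evaluable patients do not name negative specimens, although the list is open-ended.

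Section 5 admits adults "who have an injury or infection for which surgical debridement (in the operating room) followed by VAC application is planned", so infection is not required. It also states: "Patients may be on systemic antibiotics or topical antimicrobials".

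**The concern.** A zero count has no logarithm, so a t-test on log burden needs a stated value for a specimen with nothing detected. Such specimens are foreseeable at specimen 3: some wounds are injuries without infection, some patients are on antimicrobials, and the sample follows surgical debridement and wound therapy. The trial's own hypothesis is that instillation pushes burden down.

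A non-detect is also the best possible result. If it became a missing value, loss would be decided by the outcome, and a working treatment would lose more patients than its comparator. The estimated difference would shrink and power would fall in a trial with 20 per arm.

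Separately, burden is measured before therapy in every patient, but the named test makes no use of it.

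**Working it through.** **Inputs from section 12.** Alpha 0.05, power 0.80, f = 0.40. For two equal groups d = 2f = 0.80 SD.

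**The plan's own figure.** Exact noncentral-t power for a two-sided two-sample t-test with d = 0.80 and power 0.80 gives n = 25.52 per group. This reproduces "the desired sample size is 25.52" as a per-group number. At the planned 20 per arm, complete-data power is 0.69.

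**Assumptions, because the documents give no figures.** Log burden is normal with SD 1. The conventional mean is 0 and the Veraflo mean is −0.80. The conventional-arm non-detect rate p is varied.

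**Formulas if non-detects are dropped.**
- Limit: L = Φ⁻¹(p). Veraflo non-detect rate: q = Φ(L + 0.80).
- Mean of retained conventional values: φ(L)/(1 − p).
- Mean of retained Veraflo values: −0.80 + φ(L + 0.80)/(1 − q).

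At p = 0.10:
- L = −1.2816 and q = Φ(−0.4816) = 0.315.
- The retained means are 0.1755/0.90 = 0.195 and −0.80 + 0.3553/0.685 = −0.281.
- The difference is 0.195 + 0.281 = 0.476 SD against a true 0.80.
- Patients retained: 20 × 0.90 = 18.0 and 20 × 0.685 = 13.7.

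Power is by simulation with at least 20,000 replicates per t-test row; separate runs agree to about 0.01.

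| Non-detects, conventional / Veraflo | Retained of 20 | Dropped: difference, power | Kept at limit, t-test: difference, power |
|---|---|---|---|
| 1% / 6% | 19.8 / 18.7 | 0.69, 0.62 | 0.78, 0.69 |
| 5% / 20% | 19.0 / 16.0 | 0.56, 0.47 | 0.71, 0.68 |
| 10% / 32% | 18.0 / 13.7 | 0.48, 0.37 | 0.64, 0.66 |
| 20% / 48% | 16.0 / 10.3 | 0.38, 0.23 | 0.53, 0.62 |

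**Other ways of keeping the values, same four rows.**
- Rank-sum test with non-detects tied lowest (3,000 replicates): power 0.65, 0.68, 0.64, 0.65.
- Left-censored normal regression without covariate (500 replicates): power 0.70, 0.71, 0.68, 0.68; median estimate 0.80, 0.82, 0.79, 0.78.
- t-test with a constant 2 SD below the limit: difference 0.88, 1.01, 1.07, 1.10. Here the estimate is inflated.

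So at a 10% rate, one data set can give 0.48, 0.64, 0.79 or 1.07 on average, depending on a rule the plan does not state. With no true effect, type I error of the t-test after dropping and of the rank test stays near 5%.

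**Baseline covariate, no censoring.** With baseline correlation ρ, the effective difference is 0.80/√(1 − ρ²). At an assumed ρ = 0.5 this is 0.80/0.866 = 0.924, and the noncentrality is 0.924 × √(20/2) = 2.92 on 37 degrees of freedom. Power is 0.81, or about 0.80 allowing for chance baseline imbalance. At ρ = 0.3 it is about 0.73; at ρ = 0 it stays at 0.69.

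**Small-sample caution.** With 40 patients and no censoring, the likelihood-ratio cut-off of 3.841 corresponds to t² = 37 × (e^(3.841/40) − 1) = 3.73. That is |t| = 1.93 on 37 degrees of freedom, a true level of about 6%. The censored-regression powers above are therefore slightly flattering.

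**The case against.** The strongest objection is that the plan never says non-detects are excluded. A reader might infer from the t-test sentence that the cleanest wounds drop out, but the documents do not support this as a fact. The platform's result is itself described as arriving on a log scale, so a negative may come back as a floor value; if so, every patient stays in. This stands, and it makes the dilution conditional.

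A reader might also infer that the t-test is the wrong test and must give way to Wilcoxon. The table does not support that. With non-detects kept at the limit, the t-test has power 0.68, 0.66 and 0.62 at conventional-arm rates of 5%, 10% and 20%, against 0.68, 0.64 and 0.65 for the rank test. The gain comes from keeping the values.

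Nor is the direction fixed: a substitution constant far below the limit inflates the estimate. The size is not fixed either. At a 1% rate the loss from dropping is modest, and at 0% there is none.

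Finally, specimens 1 and 2 precede therapy, so treatment-dependent loss cannot arise there. The argument applies only from specimen 3 onward.

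What remains is that the primary estimate depends on an unstated choice, and that a stated method can remove this dependence and use the baseline as well.

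**Conclusion.** The point holds in conditional form. The plan gives no value for a PCR non-detect and ignores the baseline burden. If non-detects at specimen 3 or later are treated as missing, a true 0.80 SD difference is estimated at about 0.69 to 0.38 SD, and power falls from 0.69 to about 0.62 to 0.23. This rests on assumed conventional-arm non-detect rates of 1% to 20%, normal log values, a pure shift between arms and 20 per arm. The documents give no detection limit, non-detect rate or SD, so they cannot show that the loss will occur or how large it would be.

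The case for a change does not depend on that loss alone. Left-censored regression keeps every specimen and stays close to the true difference across this range, and adding the baseline could raise power from 0.69 to about 0.80 if the correlation is 0.5, an assumed value.

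**What to change.** Replace the t-test sentence in section 12 with wording such as:

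*The primary comparison is log10 bacteria per gram at specimen 3. Every specimen 3 result is kept. A non-detect is treated as left-censored at the laboratory's reporting limit. The arm difference and its confidence interval are estimated by left-censored normal regression with the specimen 1 (pre-debridement) log10 value as covariate; a specimen 1 non-detect is set to the limit and flagged by an indicator. The number of non-detects is reported by arm. A t-test or rank test with non-detects set at the limit is a sensitivity analysis.*

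Specimen 1 suits as covariate because it precedes the debridement, which itself takes place after allocation. Given the small-sample caution above, the p-value could come from a permutation of arm labels.

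The cost is one paragraph, slightly more analysis work, and obtaining from the laboratory its reporting limit and how it codes a negative result. No extra samples or patients are needed. Replacing the t-test with a rank test as the primary method is not required. The rule should be fixed before arm-level results are seen.

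### The sample size of 25.52 is a per-group figure without a label; the 40 evaluable patients planned fall 12 short of the 52 it implies, and power at 40 (about 69%) is not stated

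*Combined protocol and SAP*

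**What the plan says.** Section 12 (Data Analysis & Statistical Considerations) describes a power calculation for a one-way ANOVA with two groups, using "an alpha of 0.05, a power of 0.80, and a large effect size (f = 0.40"). The result is given as "Based on the aforementioned assumptions, the desired sample size is 25.52", with no unit.

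The next sentence says that funding was originally for 60 patients and that, once the grant had to carry indirect costs, "the sample size was decreased to 40 patients total". The planned test is given in one line: "Will use t-test for log scale of bacteria per gram".

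Section 4 (Design & Procedures) has "Two arms, 20 patients in each arm". Section 6 (Subject Recruitment and Compensation) makes clear that 40 is the number to be analysed: "A maximum of 60 subjects will be consented in order to achieve 40 evaluable subjects".

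No section gives power, or a detectable effect, for 40 patients.

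**The concern.** The word total is attached to the 40 but not to the 25.52 just before it. A reader who takes both as totals concludes that the study needs about 26 patients and will have 40, a margin of 14. If 25.52 is per group, the study needs 52 and will have 40, a deficit of 12.

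The only power figure in the document is 0.80, and it would then belong to a larger trial than the one to be run. An ethics committee, a funder or a later reader could take a null result as coming from a trial with 80% power for a large effect, when the trial never had that power.

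**Working it through.** **Inputs.** From section 12: alpha 0.05, target power 0.80, f = 0.40, two groups. From sections 4 and 6: 20 evaluable patients per arm, 40 in total. For two equal groups d = 2f = 0.80. The two-group ANOVA F test is equivalent to a two-sided two-sample t-test. The document gives no SD and no difference on the log scale, so everything below is in standardised units.

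**Step 1: reproduce 25.52.** Power is the probability that a noncentral F with 1 and N − 2 degrees of freedom and noncentrality N·f² exceeds the 5% critical value. In t form, the noncentrality is d·√(n/2) with n per group.

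- Noncentral F, solved for 80% power: total N = 51.05.
- Noncentral t, d = 0.80, two-sided, solved for 80% power: n = 25.52 per group.
- 2 × 25.52 = 51.04, which agrees with 51.05 up to rounding.

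The plan's figure is matched to two decimals as a per-group number. Rounded up, that is 26 per group, or 52 patients.

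A check by hand with the normal approximation: n = 2 × [(1.960 + 0.842)/0.80]² ≈ 24.53 per group. It runs slightly low, as expected, and is clearly also a per-group number.

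**Step 2: try the other readings.**

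- 25.52 as a total: power at f = 0.40 is 0.491, and 80% power would need f = 0.58. The stated inputs exclude this reading.
- A one-sided test at 0.05: the required size is 20.03 per group, not 25.52. The plan's figure is therefore two-sided.

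**Step 3: power at the planned size.** At N = 40 the F noncentrality is 40 × 0.40² = 6.4; in t form it is 0.80 × √10 = 2.53.

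| Total analysed | Per arm | Power at f = 0.40 |
|---|---|---|
| 40 | 20 | 0.693 |
| 52 | 26 | 0.807 |
| 60 | 30 | 0.861 |

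The normal approximation at 40 gives 0.716, so the answer does not depend on the method. The type II error at 40 is 1 − 0.693 = 0.307, against 0.20 in the sizing.

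**Step 4: effect detectable with 80% power at 40.** Solving for f gives 0.455, so d = 2 × 0.455 = 0.91, compared with the plan's 0.80.

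**Step 5: shortfall.** 52 − 40 = 12, and 12/52 = 23%. The 60 patients in sections 4 and 6 do not close this gap. They are the number consented, and the plan itself expects them to yield 40 evaluable.

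**The case against.** The calculation is not wrong: 25.52 is correct for its inputs. The plan openly reports the cut and the reason for it, and nowhere claims 80% power at 40; 0.80 enters only as an input to the sizing. A statistician can work out that 25.52 must be per group, and the original 60 exceeds 52, which suggests the authors may have read it that way themselves. Accepting lower power under a fixed budget does not make a trial invalid.

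Much of this stands. The fault is a missing unit and a missing power statement, not a computational error. But disclosing the cut is not the same as disclosing that it takes the trial below its own requirement. If the 60 originally funded were all to be analysed, the cut moved power from 86% to 69%, across the 80% target, and the text does not say so.

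A second objection is that 69% is conditional, and that is right. Tissue is sampled before therapy starts, and a baseline-adjusted comparison could recover power: about 0.73 if the correlation were 0.3, and about 0.81 if it were 0.5. These correlations are assumptions. The documents give none and plan only a t-test. A one-sided test would have 79.9% power at 20 per arm, but none is specified and the plan's 25.52 does not correspond to one.

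**Conclusion.** The concern holds. The requirement on the plan's own inputs is 26 per group (52 in total). The design delivers 20 evaluable per arm (40 in total), and the document neither labels the first figure nor gives power for the second. At f = 0.40, power is about 69% instead of 80%, and 80% power is reached only at d = 0.91 (f = 0.455).

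These figures assume equal arms, all 40 patients contributing to the analysis, and one unadjusted two-sided comparison between arms at alpha 0.05. They take f = 0.40 as given; the plan does not link it to a difference in log bacteria per gram. The conclusion concerns what the plan states about its power, not the validity of the t-test.

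**What to change.** Revise the sample-size paragraph in section 12 to read along these lines:

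> For f = 0.40 (d = 0.80), two-sided alpha 0.05 and 80% power, 25.52 patients per group are required, i.e. 26 per group and 52 in total. After the reduction to 20 evaluable patients per arm, a single unadjusted two-sided t-test has about 69% power for f = 0.40, and 80% power for d = 0.91 (f = 0.455).

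The same sentence should name the sampling time to which the t-test applies. The primary endpoint lists several, and the power figure describes only one comparison.

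No change to enrolment, test or conduct is needed. Restoring 52 evaluable patients is not being asked for: at the plan's own yield it would take 52 × 60/40 = 78 consented, above the stated maximum of 60. The only cost is that the stated power becomes less favourable.
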